## 1. Background

Adequate analgesia with maintained functionality is crucial to recovery for patients undergoing outpatient anterior cruciate ligament reconstruction. Perioperative peripheral nerve blocks have been utilized in these procedures to maximize postoperative pain, minimize side effects from IV analgesics, and facilitate discharge from PACU. The gold standard of peripheral nerve blocks for ACL reconstruction has been the femoral nerve block; however, this block has shown to have deleterious side effects such as quadriceps weakness, which has been associated with increased risk of falls and prolonged recovery postoperatively. Previous studies have focused on sparing the motor function of the quadriceps by performing adductor canal block and targeting the saphenous nerve, which is a predominantly a sensory nerve. Studies comparing efficacy of femoral nerve blocks compared to adductor canal blocks in total knee arthroplasty have shown equal analgesic action with significant sparing of quadriceps strength in the adductor canal group. Utilization of adductor canal blocks for ACL reconstruction have yielded varying results in terms of significant postoperative analgesia over non-regional based postoperative pain control. However, postoperative pain control seems to be equivalent in femoral versus adductor canal blocks in ACL reconstruction. Despite the apparent multifaceted benefit in differentiating blockade sites and duration of nerve blockade, the efficacy of continuous adductor canal blockade utilized specifically in ACL reconstruction has not been extensively studied. Studies comparing single bolus femoral nerve blocks to continuous adductor canal catheters are ongoing. The efficacy of continuous adductor canal blockade utilized specifically in ACL reconstruction compared to single bolus adductor canal blockade has yet to be determined.

## **2. Rationale and Specific Aims**

We will conduct a randomized controlled trial evaluating the efficacy of two different regional techniques in patients undergoing ACL reconstruction. The primary goal will be to determine the differences in postoperative pain on POD 2 when comparing preoperative femoral nerve block with mepivacaine plus postoperative continuous adductor canal nerve catheter with bupivacaine compared to preoperative femoral nerve block with mepivacaine plus postoperative saphenous nerve block with ropivacaine and dexamethasone. Primary outcome will be pain scores at 48hrs after PACU discharge. Secondary outcomes will include pain scores on POD 0, 1 & 3, opioid utilization on POD 0, 1, 2 & 3, and quadriceps strength on operative leg at rehab session on POD 1.

### **Hypothesis**

The use of the adductor canal continuous nerve catheter will result in lower subjective pain scores on postoperative day 2 and improved quadriceps strength on postoperative day 1.

### **Primary Aim**

1. Determine the subjective postoperative pain scores at POD 2 of preoperative femoral nerve block plus postoperative continuous adductor canal nerve catheter compared to preoperative femoral nerve block plus postoperative saphenous nerve block at 48 hours after discharge from PACU.
2. Determine the quadriceps strength of on POD 1 of preoperative femoral nerve block plus postoperative continuous adductor canal nerve catheter compared to preoperative femoral nerve block plus postoperative saphenous nerve block at 48 hours after discharge from PACU straight leg raise and knee extension tests.

### **Exploratory Aims**

1. Determine the subjective postoperative pain scores on POD 1, 2 and 3 of patients receiving (1) preoperative femoral nerve block plus postoperative continuous adductor canal nerve catheter compared to (2) preoperative femoral nerve block plus postoperative saphenous nerve block.
2. Determine the total postoperative opioid consumption on POD 1, 2 and 3 of patients receiving (1) preoperative femoral nerve block plus postoperative continuous adductor canal nerve catheter compared to (2) preoperative femoral nerve block plus postoperative saphenous nerve block.
3. Determine physical therapy participation with a validated assessment tool on POD 1.
4. Determine operative leg strength and pain at 6 weeks post-op.

## **3. Inclusion Criteria**

- A. Age 14 and older
- B. Patients who are scheduled to undergo an ACL reconstruction with patella or allograft
- C. Patient does not have a contraindication to receiving regional anesthesia

#### **4. Exclusion Criteria**

- A. Allergy to local anesthetics, dexamethasone, or adhesive tape
- B. Patients undergoing hamstring graft for ACL
- C. Preexisting infection at site of needle insertion
- D. Immunocompromised patients
- E. Preexisting sensory or motor deficit in operative extremity
- F. Patient on chronic opioid treatment.
- G. Patient having a revision of previous ACL reconstruction.
- H. Pregnancy and lactating women

#### **5. Enrollment**

We will enroll 100 patients undergoing ACL reconstruction with patella or allograft who meet the inclusion criteria stated above.

#### **6. Study Method**

Patients undergoing ACL reconstruction at Vanderbilt Bone and Joint Surgery Center by [name] will be identified at surgical scheduling and conveyed to anesthesia team for inclusion into study. The assigned in-room providers will be educated on the protocol and randomization process.

After written informed consent is obtained by either the patient or the designated surrogate decision maker, patients will be randomized to 2 groups: (1) continuous adductor canal nerve catheter or (2) long-acting single bolus adductor canal nerve block.

Following random selection via random envelope selection patients will receive the following procedures. Both groups will receive ultrasound guided femoral nerve block with 20cc of 2% mepivacaine <20 minutes prior to in room time.

Intraoperative patients will undergo initiation of general anesthesia under the care of the attending anesthesiologist assigned to the patient. Induction will include a propofol bolus and placement of laryngeal mask airway. Intraoperative opioid should be limited to no more than 150mcg of fentanyl. Upon completion of wound closure, appropriate dressing placement, emergence from anesthesia and removal of LMA, patients to be taken to PACU. Once adequately awake and alert, Group 1 patients will receive ultrasound guided adductor canal continuous nerve catheter using normal saline as bolus for placement, followed by initiation of 1/8% bupivacaine infusion through catheter at 8cc/h. Group 2 will receive ultrasound guided adductor canal nerve block with 10cc of 0.5% ropivacaine + 2mg dexamethasone (0.5cc), keeping total injectate at 10.5cc to spare significant proximal spread to femoral nerve. After adequate instruction including catheter education (if applicable) patients are to be discharged home.

The following data will be collected by evaluation by study investigators via phone calls:

- Subjective Numeric Rating Pain Scale score (NRPS) at discharge from PACU

- Subjective Numeric Rating Pain Scale score (NRPS) 48 hours following discharge from PACU.
- PONV score on POD 1 following discharge from PACU
- Subjective Numeric Rating Pain Scale score (NRPS) on POD 1 and 3.
- Opioid utilization based on number of pain pills (standardized dose) on POD 1, 2, and 3.
- Quadriceps strength in operative leg utilizing “Straight Leg Raise” Test, 0-5/5 scale.
- Quadriceps strength in operative leg utilizing knee extension, 0-5/5 scale.
- Physical Therapy participation on POD 1.
- Patient will follow up with surgeon at 6 weeks. He will do an evaluation of each patient's strength in operative leg and functional capacity in terms of ability to ambulate, as well as presence/severity of pain. Strength to be assessed by straight leg, knee extension, knee flexion on 5 point scale. Pain score on 10 point numerical scale. Ambulation: independently vs assistance, with or without pain, with or without gait abnormality

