#### **7. Reporting of Adverse Events or Unanticipated Problems involving Risk to Participants or Others**

Information regarding AEs is to be obtained and documented by the surgery center anesthesia attending and/or the investigator performing the data collection and by questioning or examining the patient. All new complaints and symptoms (i.e., those not existing prior to signing of informed consent) will be recorded on the AE CRF. All AEs will be characterized in terms of their start and stop dates, start and stop times, intensity, action taken, relationship to research study, subject outcome and whether or not the AE led to an SAE.

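### Falls are cited as a consequence of block-related quadriceps weakness, but no planned contact systematically asks about them, so fall counts by arm would be incomplete

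*Combined protocol and SAP*

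**What the plan says.** Section 1 (Background) describes the drawback of the femoral block as "quadriceps weakness, which has been associated with increased risk of falls and prolonged recovery postoperatively". It gives the motivation for the alternative as follows: "Previous studies have focused on sparing the motor function of the quadriceps by performing adductor canal block".

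Under section 6 (Study Method), every patient has a femoral block before surgery and an adductor canal technique in PACU, and then goes home. Group 1 leaves with an infusion running. The outcome list begins "The following data will be collected by evaluation by study investigators via phone calls". It covers pain scores, PONV on POD 1, pill counts, two quadriceps strength tests and physical therapy participation. The 6-week surgeon visit adds strength, pain and "Ambulation: independently vs assistance, with or without pain, with or without gait abnormality". Falls appear neither there nor in the aims and outcomes of section 2.

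In section 7, adverse-event information comes from the anesthesia attending and/or "the investigator performing the data collection and by questioning or examining the patient". The recording rule is: "All new complaints and symptoms (i.e., those not existing prior to signing of informed consent) will be recorded on the AE CRF". The section gives no fall question or definition, no schedule or time window for asking, and no comparison of safety events by arm.

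**The concern.** The plan cites a specific harm in its rationale and then leaves the recording of that harm to chance. A fall without injury, or a knee that gives way, is an event. A patient may not think of it as a complaint or a symptom, and a caller working through the section 6 list has no prompt to raise it. PONV, by contrast, was not left to general adverse-event questioning: it has its own line on POD 1.

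At stake is how a low count is read. Section 10 hopes that the results might inform standard care. If the report shows few falls or none, readers may take that as reassurance about sending patients home after these blocks. Incomplete ascertainment would not support that reading, and if completeness differed between arms, the comparison of counts would also be biased.

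**Working it through.** **1. What each planned contact asks**

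| Contact | Listed items | Falls listed? |
|---|---|---|
| PACU discharge | Pain | No |
| POD 1 | Pain, PONV, pills, quadriceps strength (day taken from section 2), PT participation | No |
| POD 2 / 48 h | Pain, pills | No |
| POD 3 | Pain, pills | No |
| 6 weeks | Strength, pain, ambulation and gait | No |
| Section 7, no schedule | New complaints and symptoms | Only incidentally |

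**2. The plan's own figure.** The only power figure is 88% for a 2-point pain difference (section 8). It cannot be reproduced, because the SD, alpha and sidedness are not given. With 50 per arm and two-sided alpha 0.05 it implies SD = 2 / [√(2/50) × (1.960 + 1.175)] ≈ 3.19. It has no bearing on falls.

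**3. What full ascertainment would give.** Inputs: 100 patients (section 5) and two arms (section 6). The allocation ratio is not stated, so 50 per arm is assumed. With 0 falls in 50, the exact upper limits are:
- one-sided 95%: 1 − 0.05^(1/50) = 5.8%
- two-sided 95%: 1 − 0.025^(1/50) = 7.1%

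**4. What incomplete ascertainment does to that limit.** Suppose each patient who falls has a probability c of having the fall recorded. The count then estimates c × (fall rate), and the one-sided limit on the fall rate becomes 5.82%/c. The documents give no value for c. As illustration, c = 0.5 gives 11.6% and c = 0.25 gives 23.3%. Since c is unknown under the current plan, no limit can be claimed.

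**5. Whether asking would settle the comparison of arms.** The documents give no fall rate, so the rates below are assumptions. Fisher power is the sum of Bin(i; 50, p₁) × Bin(j; 50, p₂) over all outcomes (i, j) with Fisher p ≤ 0.05, two-sided. The number per arm for 80% power uses the normal approximation, n = [1.960√(2p̄(1−p̄)) + 0.842√(p₁(1−p₁) + p₂(1−p₂))]² / (p₁ − p₂)², where p̄ is the mean of p₁ and p₂.

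| Assumed rates | Fisher power, 50 per arm | n per arm for 80% power |
|---|---|---|
| 2% vs 4% | 1% | 1141 |
| 2% vs 10% | 19% | 138 |
| 5% vs 10% | 6% | 435 |
| 5% vs 15% | 24% | 141 |
| 5% vs 20% | 51% | 76 |

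With no falls in one arm, the other would need at least 6 of 50 for p < 0.05 (0 vs 5: p = 0.056; 0 vs 6: p = 0.027). Full ascertainment therefore gives usable rates with intervals, but rarely a verdict between arms.

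**The case against.** The strongest reply is that section 7 already provides for questioning the patient, including by the investigator who collects the data. A fall that caused injury or pain would produce a new complaint and be recorded with dates, times and intensity. The call script and the adverse-event form are not in the documents, so their prompts are unknown. This stands as far as it goes: a reader might infer that nobody asks and no fall would be recorded, and the documents do not support that. They support only that capture is unsystematic.

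Three further readings are tempting and should not be drawn.

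- *Falls are the sole harm behind the rationale.* The Background names quadriceps weakness as the problem and gives falls as one of two consequences, with prolonged recovery. It contrasts femoral with adductor canal blocks, whereas both arms here get the same femoral block followed by an adductor canal technique. Weakness itself is measured on POD 1, as a listed primary aim, and strength again at 6 weeks. That is a fair surrogate but not a fall count, and no strength test is planned between those two points.
- *The missing question is what prevents the trial from showing which arm is safer.* With about 50 per arm, sample size would prevent it in most scenarios even if every patient were asked.
- *The stated volumes imply more falls in the catheter arm.* For Group 2 the plan speaks of "keeping total injectate at 10.5cc to spare significant proximal spread to femoral nerve", while Group 1 receives 8 cc/h and so passes that volume after 10.5/8 ≈ 1.3 hours. But one figure is a single injection and the other a cumulative slow infusion, with a different drug and concentration. Nothing in the documents says that the two spread alike, so the figures neither contradict each other nor predict a difference in falls.

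**Conclusion.** The point holds as a gap in safety ascertainment. Falls are cited in the rationale, no listed item solicits them, and the general adverse-event rule would pick them up only incidentally. Counts by arm would be incomplete to an unknown degree, and a low count could not be taken at face value. With systematic asking, 0 of 50 would support an upper limit of about 5.8% (one-sided) or 7.1% (two-sided).

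The gap is modest. It does not touch the primary pain outcome or its analysis, and closing it would yield descriptive data, not a test of which arm is safer. The limits rest on 1:1 allocation with all 50 patients per arm reached. The power figures also rest on two-sided alpha 0.05 and on assumed fall rates that the documents do not give.

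**What to change.** Add one scripted item to the POD 1, POD 2 (48 h) and POD 3 contacts and to the 6-week visit: any fall or knee giving way since the last contact (yes/no), with date and time, any injury, and whether a catheter was infusing at the time. Enter each fall on the AE CRF whether or not it caused symptoms. State in section 8 that falls will be reported by arm as counts with exact confidence intervals, as descriptive safety data without a claim of comparative safety. Report how many patients answered at each contact, so that the denominators are clear.

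The cost is one extra REDCap item and under a minute at contacts already planned, with no new visit or procedure. The remaining weakness is some recall error, chiefly over the long interval from POD 3 to 6 weeks.

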#### **8. Statistical Considerations**

Power calculations based on using 2 groups to detect a 2-point reduction in pain on numerical pain scale yields an 88% power. All individual data (including any relevant derived variables) will be stored in a password protected electronic database (REDCAP).

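### No pain score is listed before randomisation or the femoral block, so the primary 48-hour pain comparison cannot be adjusted for baseline pain and gives up some precision

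*Combined protocol and SAP*

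**What the plan says.** Section 2 of the combined protocol and SAP defines the endpoint: "Primary outcome will be pain scores at 48hrs after PACU discharge". This is a level at one time point, not a change from baseline.

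Section 6 gives the order of events. After consent, "patients will be randomized to 2 groups" by envelope. Both groups then have a femoral block, general anaesthesia and surgery. In PACU, Group 1 receives the adductor canal catheter and its infusion is started, and Group 2 receives the single-bolus adductor canal block. Patients then go home.

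The data list in Section 6 opens with "Subjective Numeric Rating Pain Scale score (NRPS) at discharge from PACU". It continues with pain at 48 hours and on POD 1 and 3, nausea and vomiting, opioid pills, quadriceps strength, physical therapy participation and a 6-week visit. No pain score before the block or before surgery is listed there or elsewhere.

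Section 8 says: "Power calculations based on using 2 groups to detect a 2-point reduction in pain on numerical pain scale yields an 88% power". It names no SD, alpha, test, model or covariate. Section 5 sets the sample size: "We will enroll 100 patients undergoing ACL reconstruction with patella or allograft".

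On strength, Section 4 excludes patients with "Preexisting sensory or motor deficit in operative extremity". At 6 weeks, Section 6 has "Strength to be assessed by straight leg, knee extension, knee flexion on 5 point scale".

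**The concern.** A baseline covariate has to be fixed before the assigned treatment can influence it. The only pain score on the day of surgery comes after both blocks, and the adductor canal step is the one that differs between the groups. Adjusting for that score could remove part of the effect the trial wants to estimate. As planned, therefore, no pain measurement can be used to reduce the residual variance of the 48-hour score, and nothing would show whether the arms differed in pain at entry.

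At stake is the width of the interval for the primary difference at a fixed 100 patients, and how far a chance imbalance in preoperative pain could move the estimate unseen. A baseline score cannot be recovered once the femoral block is in place, so the choice has to be made before enrolment.

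**Working it through.** **Inputs from the documents.** Difference to detect: 2 points (Section 8). Stated power: 88% (Section 8). Total sample: 100 (Section 5). Two groups (Section 6).

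**Assumed, because the documents are silent.** 1:1 allocation (50 per arm), two-sided alpha 0.05, no dropout, and a correlation r between baseline and 48-hour pain from 0 to 0.5.

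**Step 1: the plan's own figure.** The 88% cannot be reproduced independently, because neither the SD nor alpha is given. Only the SD it implies can be solved for. With 50 per arm, SE = SD × √(2/50) = 0.2 × SD. A two-sample t test with 98 degrees of freedom has 88% power for a 2-point difference when SD ≈ 3.16: SE = 0.632 and 2/0.632 = 3.17. The normal approximation gives SD ≈ 3.19. A one-sided test would imply about 3.52.

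**Step 2: effect of adjustment.** ANCOVA residual SD = SD × √(1 − r²), and the equivalent unadjusted sample size is 100/(1 − r²). From SD 3.158:

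| r | 1 − r² | Residual SD | Power | Equivalent patients |
|---|---|---|---|---|
| 0 | 1.00 | 3.16 | 88.0% | 100 |
| 0.1 | 0.99 | 3.14 | 88.3% | 101 |
| 0.2 | 0.96 | 3.10 | 89.2% | 104 |
| 0.3 | 0.91 | 3.01 | 90.8% | 110 |
| 0.5 | 0.75 | 2.74 | 95.2% | 133 |

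Starting from the normal-approximation SD of 3.19 gives the same powers to one decimal. The covariate costs one degree of freedom (97 instead of 98), which changes none of these powers at one decimal.

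The interval narrows by the factor √(1 − r²), whatever the SD: by about 0.5% at r = 0.1, 2% at 0.2, 5% at 0.3 and 13% at 0.5.

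**Step 3: sensitivity to the SD.** At SD 2.5, unadjusted power is already 97.7%. With r = 0.3 the residual SD is 2.5 × √0.91 = 2.38 and power is 98.6%, a gain of under one point. At SD 4, unadjusted power is 69.7%. With r = 0.3 the residual SD is 4 × √0.91 = 3.82 and power is 73.7%, a gain of 4 points.

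**Step 4: chance imbalance.** A baseline difference at the edge of the 95% range is 1.96 × √(2/50) = 0.39 baseline SDs. It would shift the unadjusted 48-hour difference by 0.392 × r × 3.158: about 0.37 points at r = 0.3 and 0.62 points at r = 0.5, or 19% and 31% of the 2-point target. This is the same variance as in Step 2 seen in a single trial, not a second loss on top of it.

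**Strength.** No comparable figure can be computed. The documents give no strength effect, SD or baseline distribution.

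**The case against.** The strongest reply is that nothing planned fails. The endpoint is a level at 48 hours, patients are randomised, and an unadjusted comparison is valid. The PACU-discharge score is a legitimate outcome that the documents never call a baseline. The correlation is not in the documents, and the SD is solved back from the stated power under an assumed alpha and allocation. At r = 0.1 the gain is 0.3 points of power, and if the true SD is nearer 2.5 there is little left to gain. Section 8 names no analysis method at all, which is a larger and separate gap. All of this stands, and it limits the point to a cheap improvement. It does not remove the point, because the score costs almost nothing and the loss from one extra covariate is negligible.

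Three stronger readings might be inferred, and the documents support none of them:

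- **That the pain comparison is biased without a baseline.** Randomisation balances preoperative pain between arms in expectation.
- **That POD 1 and 6-week strength grades confound preoperative weakness with the block effect.** Randomisation answers this in the same way. In addition, the exclusion "Preexisting sensory or motor deficit in operative extremity", if it works as written, leaves nearly everyone at or near full strength at entry, and a near-constant covariate adjusts very little. One reservation remains: the protocol does not say how a deficit is judged, and it records no grade.
- **That the 6-week strength result fails because it cannot be read as recovery.** The exploratory aim in Section 2 is strength and pain at 6 weeks, a level. Individual change cannot be calculated, but no stated analysis needs it.

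**Conclusion.** The point holds as a minor, inexpensive improvement to the primary pain analysis. No pre-treatment pain score is listed, and the earliest one listed is post-treatment, so 48-hour pain cannot be baseline-adjusted. The cost is in precision and in protection against chance imbalance; validity is not affected.

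For assumed correlations of 0.1 to 0.3, the power forgone is about 0.3 to 2.8 points; at 0.5 it is about 7 points. These figures rest on 50 per arm, two-sided alpha 0.05, no dropout and the implied SD of about 3.16, none of which the documents state. A lower true SD makes the power gain smaller and a higher one makes it larger, while the proportional narrowing of the interval depends only on the correlation.

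The point does not extend to strength as a defect.

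**What to change.** Add one item to the data list in Section 6: a numeric pain score taken after consent, before the envelope is opened and before the femoral block is placed. Scoring before the envelope is opened keeps knowledge of the allocation from influencing the answer.

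In Section 8, prespecify the primary analysis as an ANCOVA of the 48-hour pain score on treatment group and baseline pain score. Report the adjusted difference with its confidence interval, and describe baseline pain by arm.

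A preoperative strength grade on the same 0–5 scale is optional. It would document eligibility under the motor-deficit exclusion, but it probably adds little as a covariate.

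Cost: about a minute of staff time and one CRF field per patient, with no change to treatment or sample size. If the correlation turns out low, the return is small.

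### Opioid use on POD 0 is a named secondary outcome, but the collection list and exploratory aim 2 start at POD 1

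*Combined protocol and SAP*

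**What the plan says.** Section 2 (Rationale and Specific Aims) sets the primary outcome as the pain score 48 hours after the patient leaves PACU. Its secondary outcomes are pain on POD 0, 1 and 3, quadriceps strength on POD 1, and "opioid utilization on POD 0, 1, 2 & 3".

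Two other places cover opioid use after surgery, and both start a day later. Exploratory aim 2 begins "Determine the total postoperative opioid consumption on POD 1, 2 and 3 of patients receiving" and then names the two techniques. The list in section 6 (Study Method), which the investigators complete by phone, has "Opioid utilization based on number of pain pills (standardized dose) on POD 1, 2, and 3".

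That list does have a pain entry for the day of surgery, "Subjective Numeric Rating Pain Scale score (NRPS) at discharge from PACU", but no matching opioid entry. The only opioid rule for that day is a cap of 150 mcg on intraoperative fentanyl. No section says when a POD begins or ends for the pill count, or at what hours the calls are made.

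Section 6 also describes the two postoperative blocks, both given in PACU. The group 1 catheter is placed "using normal saline as bolus for placement, followed by initiation of 1/8% bupivacaine infusion through catheter at 8cc/h". Group 2 receives a single 10 mL injection of 0.5% ropivacaine with 2 mg of dexamethasone. Both groups have already had a femoral block with mepivacaine before surgery.

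**The concern.** Staff collect what the list tells them to collect. If the list omits a named outcome, that outcome is likely to be missing or to be handled differently from caller to caller: one may fold the evening of surgery into POD 1, another may leave it out. A patient can still say the next day how many pills were taken the evening before. An analyst cannot recover that at the end of the study.

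The omitted day is also not an arbitrary one. It is when one arm's infusion is only beginning while the other arm has received its full dose. An opioid comparison that starts at POD 1 does not cover those hours.

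**Working it through.** The plan gives no figure for opioid use to reproduce. Its one design figure, 88% power, concerns a 2-point pain difference and plays no part here. The check is a comparison of text, followed by short arithmetic on the blocks.

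**1. Outcomes against collection items**

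| Secondary outcome (section 2) | Days named | Items in section 6 |
|---|---|---|
| Pain | POD 0, 1, 3 | PACU discharge (POD 0), POD 1, POD 3 |
| Opioid use | POD 0, 1, 2, 3 | POD 1, 2, 3 |
| Quadriceps strength | POD 1 | two strength items, no day attached |

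For opioids, 4 days are named and 3 are listed, so 4 − 3 = 1 day, or 1 of 4, has no item. All three pain days have one.

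**2. Does any reading of POD supply the missing outcome?** The documents leave the term undefined, so take the two natural readings.

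- If each call counts pills since the previous contact, with the first counting from discharge, the day-of-surgery pills are captured but merged into the POD 1 figure. POD 0 cannot be reported separately.
- If POD means calendar day, pills taken between discharge and midnight are not counted at all.

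Neither reading gives POD 0 opioid use as section 2 names it.

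**3. How the blocks start on POD 0** (doses from section 6)

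- Catheter arm: 1/8% = 1.25 mg/mL; 1.25 mg/mL × 8 mL/h = 10 mg/h of bupivacaine, after a bolus of saline only.
- Single-injection arm: 0.5% = 5 mg/mL; 5 mg/mL × 10 mL = 50 mg of ropivacaine at once.
- Time for the infusion to deliver 50 mg: 50 / 10 = 5 h.

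These are different drugs, so equal milligrams do not mean equal effect. The arithmetic shows only that delivery differs in the first hours.

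**4. What a total from POD 1 leaves out.** Write D0, D1, D2 and D3 for the between-arm differences in opioid use on each day. The total over the days named in section 2 is D0 + D1 + D2 + D3. On the calendar-day reading, the listed items give D1 + D2 + D3. The part omitted is D0. It may be zero, positive or negative, and nothing in the documents fixes its sign or size.

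**The case against.** The strongest reply is that the protocol is not the data form. The case report form may ask about POD 0, callers may count from discharge, and opioid given in PACU may already be in the clinical record. This stands as a limit: the text shows a mismatch to reconcile, not proof that the data will be lost.

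A second reply is that section 6 and exploratory aim 2 agree, so section 2 is the outlier and could simply be corrected. That would make the protocol consistent. It would also drop a chosen outcome, on the day the blocks start differently, to save one question on a call that is already planned.

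Two stronger readings are tempting, and the documents support neither.

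- A reader might infer that leaving out POD 0 favors the catheter, because its infusion starts slowly. But the milligrams are not comparable between drugs, both arms have a femoral mepivacaine block, and no data on early pill use are given. The direction is conjecture.
- A reader might infer that the plan fails to secure an opioid total up to the primary score, which is taken "Subjective Numeric Rating Pain Scale score (NRPS) 48 hours following discharge from PACU". No section names such a total as an outcome, so its absence is not an error. Nor can the uncounted share of those 48 hours be fixed. On calendar days, discharge at 11:00 gives (24 − 11)/48 = 27%, at 17:00 (24 − 17)/48 = 15%, and at 09:00 (24 − 9)/48 = 31%. With counts since the previous contact at 24 and 48 h, it is 0%. The discharge and call times are assumptions, and these are shares of hours, not of pills.

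**Conclusion.** The point holds as an internal mismatch. One of the four opioid days that section 2 names as a secondary outcome has no item in section 6 and no place in exploratory aim 2. The loss of that outcome rests on one assumption: that the section 6 list is followed as written and the case report form adds nothing to it.

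The possible omission of an early between-arm difference is a reason to collect POD 0, not a demonstrated bias. Opioid use on POD 1, 2 and 3 can still be reported. The primary pain comparison and the planned 100 patients are not affected. This is a minor correction, worth making because it is cheap and the information is hard to recover later.

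**What to change.** - Add POD 0 to the opioid item in section 6 and to exploratory aim 2, so that both match section 2.
- At the first planned call, ask as a separate question how many pills were taken from PACU discharge to midnight on the day of surgery.
- Take any opioid given in PACU from the existing PACU record and report it as part of POD 0. Because it is not counted in pills, show it as its own component or state the conversion used.
- Define POD 1, 2 and 3 as full calendar days, and take each count once the day has ended. POD 3 should not be cut off at the time of the call. If the last call falls during POD 3, the rest of that day needs a brief follow-up the next day.

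A total from PACU discharge to the 48-hour pain score may be added if the investigators find it useful beside the primary result. It is optional.

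The cost is a few words in two places, a slightly longer first call, some recall error for the evening of surgery, a look at the PACU record and, if needed, one short contact after POD 3. The primary outcome and sample size do not change.
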